5.2 Secondary Variables

5.2.1 *Efficacy Variable*

- Body weight (age-standardized*)
- Body length (age-standardized*)
- Head circumference (age-standardized*)
- Time to full enteral or oral feeds
- Fatty acids in plasma and red blood cell membranes
- Holman index

* Anthropometric data (weight, length, and head circumference) will be standardized by age and gender according to the WHO and Fenton standards.

5.2.2 *Safety Variables*

- Adverse events (AEs)
- Length of stay in hospital (Time to discharge from hospital)
- Ratio of number of independent bloodstream infections / number of days on study medication
- Ratio of the number of patients with 1 or more bloodstream infections / number of patients on study medication
- Completion of PN treatment without lipid minimization (Yes or No)
- Withdrawal from the study due to elevated conjugated bilirubin levels (Yes or No)
- Area under the curve (AUC) of conjugated bilirubin for time periods in which levels are > 1.5 mg/dL
- Cumulative number of days of PN without lipid minimization
- Number of days until conjugated bilirubin > 2 mg/dL confirmed by a second sample collected 7 days after the first sample
- Conjugated bilirubin

Statistical Analysis Plan

FK Study Identifier: SMOF-018-CP3

- Total bilirubin
- Serum triglycerides (TGs)
- Aspartate aminotransferase (AST)
- Alanine aminotransferase (ALT)
- Gamma-glutamyl transferase (GGT)
- Alkaline phosphatase (ALP)
- Blood glucose
- Blood urea nitrogen (BUN)
- Creatinine
- C-reactive protein (CRP)
- Sterols including Phytosterols
- α -tocopherol

Statistical Analysis Plan

FK Study Identifier: SMOF-018-CP3

6 ANALYSIS SETS

The allocation of patients to analysis sets will be performed during the blinded review before database close.

The decisions done at the final BDRM shall consider carefully previous decisions which were done at the BDRM before the interim analysis to maintain consistency of allocations to analysis sets and other decisions across both stages of the entire study.

6.1 Intention-to-Treat (ITT) Analysis Set

The ITT analysis set will consist of all randomized patients. Patients will be assigned as randomized. The analysis of the primary and secondary efficacy endpoints will be performed using the ITT analysis set.

6.2 Safety Analysis Set

The safety analysis set will consist of all randomized patients who received at least one dose of study medication. Patients will be assigned as actually treated. The analysis of secondary safety endpoints will be performed using the safety analysis set.

6.3 Per Protocol Set

The per protocol set includes all patients who received study drug for at least 14 days without major protocol violations. Patients will be assigned as treated. Major protocol deviations are those that may significantly impact the completeness, accuracy, and/or reliability of the study data. A patient may be excluded from the per protocol set for, but not limited to, any of the following conditions:

- Patient does not meet critical inclusion/exclusion criteria
- Patient is removed from the study prior to day 28 for other reasons than elevated conjugated bilirubin levels
- Incorrect administration of study product

Other deviations (protocol required evaluation not completed, investigational drug issues, anthropometric measurement issues) may be judged on an individual basis.

Protocol deviations in stage 1 patients were reviewed prior to the interim analysis according to the Data Review Plan (Version 1.0, 15 February 2019). Results of the interim BDRM were documented in the Protocol Deviation Listing dated 12 July 2019.

Statistical Analysis Plan

FK Study Identifier: SMOF-018-CP3

Protocol deviations in both study stages and exclusion of patients from the per-protocol set for the final analysis were reviewed in the BDRM before final analysis on October 28, 2020, and will be documented in the minutes of the BDRM and the Protocol Deviation Listing (date not yet available).

The analysis of the primary and secondary efficacy endpoints will be performed using the per protocol set.

Version (of CSP): 3.0

CONFIDENTIAL

page 25 of 56

date: 5 OCT 2020

Annex No.: [REDACTED]
Document No.: [REDACTED]

00
1

Date:
Page:

[REDACTED]
25 of 56

Statistical Analysis Plan

FK Study Identifier: SMOF-018-CP3

7 STATISTICAL CONSIDERATIONS AND DEFINITIONS

All data will be evaluated descriptively and in an exploratory way. Point estimates of differences between treatment groups and corresponding two-sided 95%-confidence intervals will be presented for the primary and key secondary efficacy endpoints. Statistical hypotheses will not be tested and p-values will not be reported.

The analysis of the primary and secondary efficacy endpoints will be performed using both the ITT analysis set and the per protocol set. The analysis of the secondary safety endpoints will be performed using the safety set.

Descriptive statistics will be displayed to provide an overview of the efficacy and safety results by treatment group, stratum and overall. For categorical parameters, these will consist of the number and percentage of patients in each category. The denominator for percentages will be based on the number of patients in the corresponding analysis set, missing will be displayed as a category. For continuous parameters, descriptive statistics will include number of patients with number of non-missing values, mean, standard deviation, median, minimum, and maximum.

7.1 Changes in the Conduct of the Trial or Planned Analysis

The study was terminated early after the interim analysis and consultancy with the FDA. Changes in statistical analysis are described in this document and the Study Protocol Version 3.0.

7.2 Statistical Software

The statistical analysis will be performed using SAS version 9.4.

7.3 Protocol Deviations/Data Review

After all queries issued and answered to the extent possible, all medical codes are approved, all SAEs are reconciled, and prior to locking and unblinding the database for the final analysis, the sponsor will convene a BDRM.

The primary purpose of the BDRM will be to resolve outstanding data issues, to access and define the handling of missing data, to examine and classify major and minor protocol deviations, to define the analysis sets, and to finalize other statistically related issues. The final allocation of patients to analysis sets will be performed during the blinded review as described in Sections 4.6 and 6.

7.4 Handling of Drop-outs

Dropouts (not early dropouts, see Section 7.5) are patients who are withdrawn after randomization and receiving any study drug. Dropouts were not to be replaced. The number of dropouts and reason of dropout will be tabulated by treatment group.

7.5 Procedures for Replacement of Patients

Patients withdrawn from study after randomization but before receiving any study drug will be counted as “early drop-outs”. These patients will be replaced and will not have any additional assessments.

7.6 Adjustment for Covariates / Strata

The randomization is stratified by underlying disease (No NEC vs. NEC). The analysis of the primary endpoint will be stratified by underlying disease.

7.7 Multi-center Trials

The randomization was stratified by study site. The primary endpoint will be summarized descriptively by treatment group and site.

7.8 Multiple Comparison

As all analyses are descriptive and exploratory and no statistical hypotheses will be formally tested, multiplicity will not be taken into account.

7.9 General Calculation Rules

Unless stated otherwise, the term “descriptive statistics” refers to the total number of patients in the analysis set, the number of non-missing values, mean, median, standard deviation, minimum, and maximum for continuous data and frequencies and percentages for categorical data. Minimum and maximum values will be rounded to the precision of the original value, means and medians will be rounded to 1 decimal place greater than the precision of the original value, and standard deviations will be rounded to 2 decimal places greater than the precision of the original value. Precision of AUC will be four significant digits (e.g., 123.2 or 1.456 depending on the range of the values). Percentages will be rounded to one decimal place. For categorical variables, categories with no patients or all patients should be indicated by 0% and 100%. Unless otherwise stated confidence intervals will be two-sided with 95 % confidence level and will be presented with the same precision of the estimated parameter.

Statistical Analysis Plan

FK Study Identifier: SMOF-018-CP3

Unless otherwise noted, all data collected during the study will be included in data listings and will be sorted by treatment group, site and patient number and then by date/time for each patient number.

Baseline values for efficacy and safety variables will be based on the last non-missing data collected prior to the first administration of clinical trial material (CTM), unless otherwise noted.

Study days on or after the initial dose of CTM will be computed as

Study Day = Date – Study Drug Start Date + 1.

Study week is the sequence of 7 consecutive study days 1-7, 8-14, 15-21, 21-28, 29-35 ... starting at Study Day 1 (baseline).

For pre-dosing dates, study days will be computed as Study Day = Date – Study Drug Start Date.

Age will be calculated from the date of informed consent.

7.10 Handling of Missing Data and Outliers

Missing data imputation is planned for both intention-to-treat and per protocol analysis. The distribution of missing value pattern, the appropriateness of imputation rules as well as the potential introduction of bias will be investigated at the BDRM. Also, the impact and handling of outliers will be discussed at the BDRM.

The following table shows the anticipated missing data patterns and the pre-specified imputation approach for the primary endpoint:

Statistical Analysis Plan

FK Study Identifier: SMOF-018-CP3

Missing Data Patterns and Imputation Approach for the Primary Endpoint

Missing Data Pattern of Conjugated Bilirubin	Imputation Approach for Primary Endpoint
A) Some missing value(s) and at least one value > 2mg/dL	
1. Value > 2mg/dL is confirmed	Primary endpoint met.
2. Value > 2mg/dL but not confirmed due to missing value	Primary endpoint met.
B) Some missing value(s) and all non-missing value(s) are <= 2mg/dL	
3. Value available on D28	Primary endpoint not met.
4. Latest value available on D22	Primary endpoint met if value > 1.5 mg/dL on D22. Otherwise, the primary endpoint will not be considered met.
5. Latest value available on D15	Primary endpoint not met if latest value <=1.5 mg/dL. Otherwise, imputation will depend on - Reason for dropout or missing data (adverse event/withdrew consent/weaned off before D28/lost to follow-up/death) - Conjugated bilirubin level(s) and trend
6. Latest value available only before D15 or no data available	Primary endpoint not met if latest value <=1.5 mg/dL. Otherwise, imputation will depend on - Reason for dropout or missing data (adverse event/withdrew consent/weaned off before D28/lost to follow-up/death) - Conjugated bilirubin level(s) and trend
C) All values missing	Primary endpoint not met.

In particular, for cases A2, B3, B4, and C information on missing conjugated bilirubin values (e.g. timing) and conjugated bilirubin levels over time as well as the reason for dropout or missing data will be reviewed for each patient during the BDRM and an individual decision for imputation will be taken.

Statistical Analysis Plan

FK Study Identifier: SMOF-018-CP3

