7.2 Rationale of Study Design, Including Choice of Control Group

Fresenius Kabi has been requested to perform a study demonstrating **superiority of Smoflipid compared to Intralipid in terms of a safety benefit** as reflected by changes in biochemical markers of liver health.

Long-term use of PN in neonates is sometimes associated with hepatic complications, including biochemical alterations (i.e., elevated bilirubin and transaminases) considered to be markers for early cholestasis (Colomb, et al. 2000, Javid, et al. 2011, Koseesirikul, et al. 2012, Pichler, et al. 2012). These biochemical alterations may worsen with prolonged PN and lipid administration and are more prevalent in neonates born at an early gestational age or in neonates with a surgical condition (Christensen, et al. 2007, Gura, et al. 2008, Javid, et al. 2011, Koseesirikul, et al. 2012).

The incidence of cholestasis in neonates receiving PN for 14 to 28 days ranges from 14% to 33%, depending on the underlying disease (Christensen, et al. 2007). Javid and colleagues reported a median time to cholestasis (defined as 2 consecutive bilirubin levels > 2 mg/dL obtained within 14 days) of 23 days in the groups of surgical neonates and 77% of the infants who developed cholestasis did so within 5 weeks of PN (Javid, et al. 2011). Consequently, a safety benefit of Smoflipid will only become visible, on average, after at least 3 weeks of PN.

The median time of exposure to PN in this patient group has been reported to be 28 days, with approximately 15% of patients still receiving PN after 3 months (8% after 6 months) (Javid, et al. 2011). As the number of patients on PN in a given population decreases over time, it may

Clinical Study Protocol SMOF-018-CP3 **Smoflipid 20% lipid injectable emulsion**

be difficult to enroll enough patients who receive PN for more than 28 days to identify a statistically significant difference.

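### SAP 7.10 scores infants who withdraw or are lost on PN by Day 15 with a low bilirubin as cholestasis-free, whatever the reason, which understates their 28-day risk in the ITT analysis

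*SAP*

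**What the plan says.** SAP 7.10 imputes the primary endpoint by missing-data pattern. Row B5 covers infants whose last value is on Day 15. Row B6 is labelled "Latest value available only before D15 or no data available". Both carry the same rule: "Primary endpoint not met if latest value <=1.5 mg/dL. Otherwise, imputation will depend on" the reason for leaving and the bilirubin trend. The reasons listed include withdrawn consent, loss to follow-up, weaning and death, but they come into play only above 1.5 mg/dL.

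The section then names patterns for a patient-by-patient decision: "In particular, for cases A2, B3, B4, and C information on missing conjugated bilirubin values" and the reason for dropout are to be reviewed. B5 and B6 are not named. More generally, "the appropriateness of imputation rules as well as the potential introduction of bias will be investigated at the BDRM", with no alternative rule fixed.

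SAP 8.10 summarises the combined stages with and without imputation, for the ITT and per protocol sets. SAP 7 sets the general denominator: "The denominator for percentages will be based on the number of patients in the corresponding analysis set, missing will be displayed as a category".

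On timing, Protocol 7.2 cites a median time to cholestasis ("obtained within 14 days) of 23 days in the groups of surgical neonates") and says that 77% of infants who "developed cholestasis did so within 5 weeks of PN". It concludes: "Consequently, a safety benefit of Smoflipid will only become visible, on average, after at least 3 weeks of PN".

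**The concern.** Protocol 10.3 excludes infants with conjugated bilirubin above 0.6 mg/dL, and Protocol 5.1 expects elevations after roughly two to three weeks of PN. A Day 8 or Day 15 value at or below 1.5 mg/dL is therefore the expected early course and says little about Day 28. For an infant weaned to enteral feeds, scoring the endpoint as not met is sensible. For one withdrawn or lost while still on PN, it sets the remaining risk to zero over the period in which the protocol expects much of the cholestasis.

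Two results are at stake: the absolute 28-day risk in the ITT set and, if such leaving differs by arm, the relative risk. With hypothesis testing dropped (SAP 4.5), the estimate and its interval are the whole result.

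**Working it through.** **The plan's own figures.** The plan prints no size for this rule. Its Table 1 sample sizes reproduce exactly (47, 124, 66, 176 and 264 per group; pooled-variance chi-square, one-sided 0.025, 80% power), but they do not bear on the rule.

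**Inputs.** Protocol 7.2 gives two points on the onset curve among cases: F(23) = 0.50 and F(35) = 0.77, with t in days of PN. Assumption: PN starts near study Day 1. The share leaving early (d) is not in the documents and is assumed.

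**Share of cases still to come.** For a last sample on day t and horizon H, s = 1 − F(t)/F(H).

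- Weibull through both points: F(t) = 1 − exp[−ln2·(t/23)^k], with k = ln(−ln 0.23/ln 2)/ln(35/23) = 1.79. F(8) = 0.099, F(15) = 0.276, F(29) = 0.650.
- Constant hazard with the same median: F(t) = 1 − 2^(−t/23). F(8) = 0.214, F(15) = 0.364, F(29) = 0.583. This gives F(35) = 0.65, so it misses the 77% figure; it is kept as a low bound.
- Log-normal, log-logistic and straight-line interpolation, each through both points.

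| Curve | Horizon | After Day 8 | After Day 15 |
|---|---|---|---|
| Weibull | Day 29 | 85% | 58% |
| Constant hazard | Day 29 | 63% | 38% |
| Log-normal | Day 28 | 95% | 64% |
| Log-logistic | Day 28 | 93% | 65% |
| Straight line | Day 28 | 72% | 47% |

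Changing the horizon by one day moves a share by at most 2 points.

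**Effect on the recorded risk.** If a share d of the arm leaves on PN and is scored not met, recorded risk = p(1 − d·s), a loss of p·d·s. With d = 10%:

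- p = 0.33 (top of the protocol's 14% to 33% range): 0.33 × 0.10 × 0.38 = 1.3 points, up to 0.33 × 0.10 × 0.95 = 3.1 points.
- p = 0.14: 0.5 to 1.3 points.

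**Effect on the relative risk (Smoflipid/Intralipid).** Recorded RR = RR × (1 − dS·s)/(1 − dI·s), where dS and dI are the shares leaving in each arm. With true RR 1.00, dS = 10% and dI = 20%:

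- Leaving at Day 8, Weibull: (1 − 0.0847)/(1 − 0.1694) = 1.10. At p = 0.30 the recorded risks are 27.5% and 24.9%.
- Leaving at Day 8, constant hazard: (1 − 0.063)/(1 − 0.126) = 1.07.
- Leaving at Day 8, log-normal (the steepest early rise): (1 − 0.095)/(1 − 0.190) = 1.12.
- Leaving at Day 15: (1 − 0.058)/(1 − 0.116) = 1.07 (Weibull); (1 − 0.038)/(1 − 0.076) = 1.04 (constant hazard).
- dS = dI: the factor is 1 and the RR is unchanged.

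Exchanging the arms inverts these ratios and favours Smoflipid.

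**The case against.** The strongest objections concern how far the point reaches.

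*Deaths.* A reader might infer that the rule counts death as a good outcome and conflicts with SAP 8.12.1.2, where death is a competing risk. It does not conflict. In a competing-risk cumulative incidence, an infant who dies event-free never adds an event, which is the same contribution as not met. Deaths need to be shown beside the result, not rescored.

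*Overall direction.* A reader might infer that the primary incidence is biased downward in both arms. The documents do not support that. Row A2 (unconfirmed value above 2 mg/dL) and row B4 (above 1.5 mg/dL on Day 22) impute met and push the risk up.

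*Most cases after Day 15.* A median of 23 days does put most of all cases there. Within the 28-day endpoint it depends on the curve: 38% and 47% under two of the five.

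*Existing safeguards.* These are real but partial:

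- The per protocol set needs at least 14 days of drug, and removal before Day 28 for reasons other than bilirubin is a listed ground for exclusion. The effect therefore falls mainly on the ITT set.
- The list of patterns for individual decision opens as examples, and the blinded review will consider bias. But nothing commits it to look at B5 or B6.
- SAP 8.12.1.2 already plans an Aalen cumulative incidence that censors living event-free infants. It is secondary, uses the safety set, censors at last follow-up rather than last sample, and specifies no Day-29 risk or risk ratio.
- The unimputed percentage shows missing infants as a category but, under SAP 7, keeps them in the denominator, so it need not remove the dilution. Whether they count as non-events in an unimputed Mantel-Haenszel relative risk is not stated.

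*Size.* The leaving rates are assumed. Many early stoppers may be weaned infants, for whom the rule is sensible. PN before enrolment is allowed, which would move onset earlier in study time and shrink the effect.

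**Conclusion.** The concern stands for one group: infants who withdrew or were lost while on PN, with a last value of at most 1.5 mg/dL on or before Day 15. The rule gives them no later risk, although about 38% to 65% of 28-day cases arise after Day 15 and 63% to 95% after Day 8, depending on the assumed curve. Their contribution to the ITT risk is understated, by about 1.3 to 3.1 points of the arm's risk at a true risk of 33% with 10% leaving. The relative risk shifts in favour of the arm with more such leavers: about 1.07 to 1.10 (1.12 under the log-normal curve) at an assumed 10% versus 20% leaving at Day 8 with equal true risk, less for leaving at Day 15, and not at all with equal loss. The true size cannot be known without the B5 and B6 counts. Because the analysis is descriptive, the harm is a biased estimate and interval, not a false test result. It merits correction because the remedy is cheap.

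**What to change.** 1. SAP 7.10: in rows B5 and B6, keep the automatic not met for infants weaned to enteral feeds and for deaths. For infants withdrawn or lost while on PN, extend the review of reason and trend to values at or below 1.5 mg/dL, and add these cases to the patterns named for individual decision.
2. SAP 8.10: beside Table 14.2.1.1, add an ITT Day-29 cumulative incidence of the confirmed event by arm and NEC stratum, with the risk ratio and 95% CI. Use the Aalen estimator as in 8.12.1.2, with death as a competing event. Keep weaned event-free infants as non-events to Day 29; censoring them at weaning would give them the later risk of infants still on PN. Censor only infants withdrawn or lost on PN, at their last bilirubin sample.
3. Print the B5 and B6 counts by reason and arm, including deaths.

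The cost is some SAP wording, one more estimate with a method already planned, and slightly wider intervals. The added estimate assumes that censored infants resemble those still followed in the same arm and stratum; the SAP should say so. The change should be settled before the final unblinding.

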7.10.1 Missing Severity or Causality of AEs

Missing severity will not be imputed but counted as a separate category. AEs which are not rated as “not related” will be reported as related according to the study protocol and sponsor standards.

7.10.2 Date Values

In cases of incomplete dates (e.g., pertaining to AE, concomitant medication, medical history, etc.), the missing component(s) will be assumed as the most conservative value(s) possible.

For example, if the start date has a missing day value and year and month are available, the first day of the month but not before first intake of study medication will be imputed for study day computations (i.e., treatment-emergent status, etc.). The start date will be set to the first day of the year but not before first intake of study medication if month and day are missing and year is available.

If day is missing for an end date, the last day of the month will be imputed. Similar logic will be assumed for missing month and year components.

Date imputation will only be used for computational purposes e.g., treatment-emergent status, etc. Actual data values as they appear in the original CRFs will be shown in the data listings.

7.10.3 Non-date Values

Every effort will be made to obtain the protocol-required data for all study assessments that are scheduled for each scheduled visit for all patients who have been enrolled.

Missing values will be reviewed and methods how to handle these missing data in the analysis will be discussed in the BDRM.

7.10.4 Handling of Outliers

Potential outliers will be clarified during the data cleaning process.

